#### RE AND POST SUBJECT ENROLLMENT

*Physicians will complete the Substance Abuse Attitudes Survey, the Physicians WorkLife Survey and the optional Qualitative Interview prior to first participant enrollment at the site and after the last participant enrollment at the site.*

*Physicians will also be given the opportunity to participate in a voluntary interview regarding policies and procedures of DCF reporting issues at their clinics. Interviews will be conducted once sites are trained on the study.*

Interviews will be audiorecorded and identified by a subject number only. Interviews will be transcribed and any identifying information pertaining to the provider or the clinic will be removed. Upon completion of transcription, audiorecordings will be destroyed. All notes, audio recordings and transcriptions will be stored in YaleBox, a password protected, secure cloud storage system. Only members of the study team will have access to this system.

Interviews will be conducted on approximately 10 to 15 randomly selected providers. Consent for interviews will be obtained using a verbal consent which will be read to providers prior to beginning the audiorecording. Verbal consent will be used in lieu of written consent as a signed consent would be the only PHI linking the provider to the transcript.

Compensation for interviews will be a \$50 Amazon egift card.

## 8.2 SAFETY ASSESSMENTS

Assessment of Adverse Events- Participants will be asked about any events that meet the definition of an AE listed below at each study contact. This information will be recorded in the eCRF.

## 8.3 ADVERSE EVENTS AND SERIOUS ADVERSE EVENTS

### 8.3.1 DEFINITION OF ADVERSE EVENTS

This protocol uses the definition of adverse event from 21 CFR 312.32 (a): any untoward medical occurrence ***whether or not it is considered related to participation in the study.***

### 8.3.2 DEFINITION OF SERIOUS ADVERSE EVENTS

A serious adverse event is any adverse event that results in one of the following:

1. Results in death
2. Is immediately life-threatening
3. Requires in-patient hospitalization (other than for expected delivery or other anticipated obstetrical procedures unrelated to participation) or prolongation of existing hospitalization (other than for anticipated obstetrical reasons, e.g., cesarean section).
4. Results in persistent or significant disability or incapacity
5. Results in a congenital abnormality or birth defect
6. Is an important medical event that may jeopardize the subject or may require medical intervention to prevent one of the outcomes listed above

As with AEs, SAEs do not have to be related to participant in the study. For example, if the participant is in a car accident and is hospitalized, that is considered an SAE and should be recorded. It is important to note, that not all SAEs need to be reported to IRBs. Please see details below.

### 8.3.3 CLASSIFICATION OF AN ADVERSE EVENT

#### 8.3.3.1 SEVERITY OF EVENT

Adverse events will be graded according to the following guidelines.

- **Mild** – Events require minimal or no treatment and do not interfere with the participant's daily activities.
- **Moderate** – Events result in a low level of inconvenience or concern with the therapeutic measures. Moderate events may cause some interference with functioning.
- **Severe** – Events interrupt a participant's usual daily activity and may require systemic drug therapy or other treatment. Severe events are usually potentially life-threatening or incapacitating. Of note, the term "severe" does not necessarily equate to "serious".

#### 8.3.3.2 RELATIONSHIP TO STUDY INTERVENTION/EXPERIMENTAL MANIPULATION

All adverse events (AEs) will have their relationship to study procedures, including the intervention, assessed by an appropriately-trained clinician based on temporal relationship and his/her clinical judgment. The degree of certainty about causality will be graded using the categories below.

- **Related** – The AE is known to occur with the study procedures, there is a reasonable possibility that the study procedures caused the AE, or there is a temporal relationship between the study procedures and the event. Reasonable possibility means that there is evidence to suggest a causal relationship between the study procedures and the AE.
- **Not Related** – There is not a reasonable possibility that the study procedures caused the event, there is no temporal relationship between the study procedures and event onset, or an alternate etiology has been established.

#### 8.3.3.3 EXPECTEDNESS

Given the population of study participants the following AE are expected and will not be recorded as part of the study. Examples of this include hospitalization for delivery with or without complications. Deliveries are expected events and adverse birth complications are not uncommon in this population. This relates to the substances that are misused and not to the randomization of support systems.

Women on medication for OUD commonly deliver babies that are small for gestational age or early and this can be due to the medication, the earlier misuse of an opioid or use/misuse of other substances. Provision of medication for an OUD is recommended treatment outside of the study.

Other common and expectable events include delivery of infants who require admission to a neonatal intensive care or step-down unit. Again, this is a common event among women who use substances, including opioids and medication for OUD.

Women may live in poverty or confront violence. Sadly, this is not uncommon in this population so events such as assault, even if it culminates in hospitalization, would not be considered a severe AE related to the study conditions.

Women with OUD commonly have comorbid problems with conditions such as depression and post-traumatic stress disorder. The presence of these conditions or symptoms of these conditions would not be attributable to this trial given that they are common outside of the trial and nothing in the trial promotes the onset or maintenance of these problems.

An example of an event related to the trial would be that the participant is upset by the questions that are asked of the participant. In this instance, every attempt will be made to discuss this with the patient and provide care and treatment for their distress related to this.

Another example of an event related to the trial would be a breach of confidentiality. Although we will add measures to minimize this risk, should it occur we will take corrective measures with the study team member who is responsible and/or modify systems to decrease the likelihood of a breach.

---

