H2: Babies born to mothers treated in CC centers will have higher birth weights on average compared to babies born to mothers treated in ECHO centers.

- 3) To determine differences in obstetrical providers' work satisfaction among the two treatment models according to the **Physicians Worklife Survey**.

H3: Obstetrical providers randomized to the CC compared to the ECHO condition will score higher on subscales (autonomy, relationship with patients, patient care issues and relationship with staff) of the Physicians Worklife Survey.

Primary, secondary and exploratory outcomes are listed in the table below:

Outcome	Type of Outcome	Assessment Tool	Assessment timepoints	Sample size
Treatment engagement	Primary	Medical records and study database	Prenatal treatment period	264

Treatment retention	Primary	Medical records and study database	Birth and 3-months post-partum	264
Patient Activation	Primary	Patient Activation Measure	Baseline, 26 weeks ,36 weeks and 3 months post-partum	264
#/% initiated onto MAT	Secondary	Medical records and study database	Prenatal treatment period	264
#/% retained on MAT	Secondary	Medical records and study database	Birth	TBD
Birth weight	Secondary	Medical records and study database	Birth	264
Physician Work Satisfaction	Secondary	Physician Work Life Survey	Before first participant enrollment and after last participant enrollment	12
#/% increasing at least one PAM level	Secondary	Patient Activation Measure	Week 36 and 3-months post-partum	264
#/% offered MAT	Exploratory	Medical records and study database	Prenatal treatment period	264
#/% continuing MAT at 3 months postpartum	Exploratory	Medical records and study database	3-months post-partum	TBD
#/% engaging in an opioid treatment program at 3 months post delivery	Exploratory	Medical Records and study database	3-months post-partum	264
#/% abstinent from illicit opioids or misuse or prescription opioids	Exploratory	a. TLFB b. Urine Drug screens	a. monthly b. each prenatal visit and birth and post birth	264
#/% with concurrent substance use	Exploratory	a. TLFB b. Urine Drug screens	a. monthly b. each prenatal visit and birth and post birth	264
Low birth weight	Exploratory	Medical records and study database	birth	264
Resuscitation at delivery	Exploratory	Medical records and study database	birth	264
Fetal demise	Exploratory	Medical records and study database	birth	264
Preterm birth	Exploratory	Medical records and study database	birth	264

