## 8.1.6 BIRTH

- *Birth Outcomes-* Birth outcomes will be collected through review of the patient's medical record including low birth weight, resuscitation at delivery, fetal demise, preterm birth, duration of hospitalization.

---

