#### 8.3.4 TIME PERIOD AND FREQUENCY FOR EVENT ASSESSMENT AND FOLLOW-UP

The occurrence of an adverse event (AE) or serious adverse event (SAE) may come to the attention of study personnel during study visits and interviews of a study participant presenting for medical care, or upon review by a study monitor.

All AEs, not otherwise precluded per the protocol, will be captured on the appropriate case report form (CRF). Information to be collected includes event description, time of onset, clinician's assessment of severity, relationship to study procedures (assessed only by those with the training and authority to make a diagnosis), and time of resolution/stabilization of the event. All AEs occurring while on study will be documented appropriately regardless of relationship. All AEs will be followed to adequate resolution.

Any medical or psychiatric condition that is present at the time that the participant is screened will be considered as baseline and not reported as an AE. However, if the study participant's condition deteriorates at any time during the study, it will be recorded as an AE.

At each study visit, the investigator will inquire about the occurrence of AE/SAEs since the last visit.

---

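### Neonatal intensive-care admission and maternal delivery complications are kept out of adverse-event recording and named as outcomes nowhere, so a difference between arms could go unseen

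*Combined protocol and SAP*

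**What the plan says.** Section 8.3.3.3 (Expectedness) opens with a rule about recording, not only about reporting: "the following AE are expected and will not be recorded as part of the study". It illustrates the rule: "Examples of this include hospitalization for delivery with or without complications". Two paragraphs later it extends the list: "Other common and expectable events include delivery of infants who require admission to a neonatal intensive care or step-down unit". Its lead-in reason is that the events are expected in this population. It then adds a causal reason: "This relates to the substances that are misused and not to the randomization of support systems".

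Section 8.3.4 points both ways. It limits case-report-form capture to adverse events that the protocol does not preclude, but the same paragraph states: "All AEs occurring while on study will be documented appropriately regardless of relationship". Section 8.3.2 separately takes expected delivery admissions and anticipated obstetrical procedures out of the hospitalization criterion for a serious adverse event.

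On the outcome side, Section 3 hypothesises: "Babies born to mothers treated in CC centers will have higher birth weights on average". Section 8.1.6 takes these items from the medical record: "low birth weight, resuscitation at delivery, fetal demise, preterm birth, duration of hospitalization". Section 9.4.8 compares the same five between care models. Section 4.1 also provides for extraction of maternal, fetal and neonatal outcomes, without itemising them.

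The Safety Oversight section gives the DSMB the types of adverse and serious adverse events. It also lets members ask for other elements and see de-identified data if needed.

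**The concern.** An event can be expected in a population and still occur more often in one arm. Expectedness is a sound reason to waive individual forms and expedited reports. It is not a reason to leave an event uncounted, because only a count by arm can show a difference. Presuming that the events are unrelated to randomization also settles in advance a question that the trial is meant to inform.

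The stake is safety information about mothers and infants in a population for which the protocol itself judges a DSMB necessary. If an event class is outside the adverse-event system and is not an outcome either, neither the board nor the final report is assured of a count by arm.

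**Working it through.** There is no stated figure to reproduce, and no arithmetic applies beyond a count. The check sets the sections side by side.

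**Step 1. Does the rule stop recording, or only expedited reporting?** The wording in 8.3.3.3 is about recording. Section 8.3.4 gives it effect by admitting to the form only events not precluded elsewhere. The delivery example falls directly under the rule. Intensive-care and step-down admission falls under it by reading the later paragraph as a continuation of the list, which is how it is worded.

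**Step 2. Is the causal reason compatible with the rest of the protocol?** It conflicts in three places.

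- Sections 3 and 9.1 state a directional hypothesis that CC increases mean birth weight.
- The Benefits part of Section 2.3.3 says CC shows promise in lessening the maternal and fetal consequences of illicit opioid use and in reducing use of other harmful substances.
- Section 8.3.3.3 itself says that small or early babies may result from the medication for opioid use disorder. Sections 3 and 9.1 hypothesise that CC increases engagement and retention in that treatment. The arms are therefore expected to differ in an exposure that this section names as a possible cause.

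Section 8.3.3.2 also asks a trained clinician to judge the relationship of every adverse event to study procedures. Section 8.3.3.3 replaces that with a blanket judgement for this class.

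**Step 3. Which birth harms are captured elsewhere?**

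| Event | Adverse-event form (8.3.3.3) | Named outcome (1.3, 3, 8.1.6, 9.4.8) |
|---|---|---|
| Birth weight | not an event | yes, secondary |
| Low birth weight, preterm birth, fetal demise, resuscitation | excluded where they count as complications of delivery | yes, exploratory |
| Duration of hospitalization | excluded for the delivery admission | yes, exploratory |
| Neonatal intensive-care or step-down admission | excluded | **no** |
| Maternal complications of delivery | excluded | **no** |

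Six birth outcomes are named (birth weight plus five), each with a listed sample size of 264. The last two rows are named nowhere. Duration of hospitalization is only a partial proxy for an intensive-care admission, because a long stay need not involve intensive care and a short admission need not lengthen the stay much.

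**Step 4. What does the DSMB receive?** By default it receives types of adverse and serious adverse events. The named birth outcomes can be requested, but no table of them by arm is specified. For the two unnamed classes, a request succeeds only if the unitemised extraction in Section 4.1 happens to include them.

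**Step 5. Are 8.3.2, 8.3.3.3 and 8.3.4 consistent?** The capture sentence in 8.3.4 anticipates exclusions, and the carve-out in 8.3.2 covers delivery admissions. However, that carve-out sits in the hospitalization criterion alone. A life-threatening complication of delivery would still meet another criterion in 8.3.2, while 8.3.3.3 excludes complicated delivery admissions without qualification. The second sentence quoted from 8.3.4 admits no exclusions at all.

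**The case against.** The strongest reply is that the study, as distinct from the adverse-event form, already collects most of these harms. This stands. Preterm birth, fetal demise, resuscitation, low birth weight and length of stay are extracted and compared by model. A reader might infer from 8.3.3.3 that birth harms go unrecorded altogether. The documents do not support that.

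Second, a reader might infer that the DSMB has no means of comparing these events by arm. That is also too strong, because members may ask for other elements and see de-identified data. What is missing is a default table and, for two event classes, an assured source for one.

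Third, a reader might extend the exclusion to assault, depression and post-traumatic stress. For these, 8.3.3.3 speaks of severity, relatedness or attribution to the trial. It does not repeat that they go unrecorded. Section 8.3.4 records deterioration of a baseline condition as an adverse event, and the Edinburgh depression scale is collected through three months postpartum. The point is therefore confined to delivery and neonatal events.

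Fourth, the extraction in Section 4.1 is broad, and the list in 8.1.6 need not be exhaustive, so the two missing items may in practice be abstracted. That is possible, but nothing in the plan secures it.

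Finally, the trial compares two ways of supporting clinicians, and its research procedures are described as minimal risk. How much obstetric morbidity to route through adverse-event forms is partly a matter of preference. That supports capturing these events by record extraction rather than on individual forms. It does not support leaving them unnamed.

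**Conclusion.** The point holds in a limited form. As written, 8.3.3.3 removes neonatal intensive-care or step-down admission and maternal delivery complications from adverse-event recording, and no other section names them as outcomes. Part of the justification, that they are unrelated to the randomized model, conflicts with the trial's own hypotheses. A difference between arms in these two event classes could therefore go unseen by both the DSMB and the final report.

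The size cannot be computed. The protocol calls neonatal admissions common and birth complications not uncommon, but it gives no rates. It would be tempting to call them the most frequent serious events in the trial; no figure supports that, and 8.3.2 does not count an ordinary delivery admission as serious.

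The conclusion assumes that sites follow 8.3.3.3 as written and that the extraction in Section 4.1 does not already include both items. If an extraction form or DSMB charter outside these documents covers them, what remains is a correction of wording. The primary outcomes are not affected. The change should be made, but the trial's main conclusions do not depend on it.

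**What to change.** 1. **Section 8.3.3.3:** state that expected delivery and neonatal events are exempt from individual adverse-event forms and from expedited reporting only, and that they are captured by record extraction. Delete the sentence presuming that they are unrelated to the randomized model.
2. **Section 8.1.6:** add neonatal intensive-care or step-down admission, and maternal complications of delivery, to the items extracted, with a short definition of each. Carry them into footnote 7 of Section 1.3 and the list in Section 9.4.8.
3. **Safety Oversight and reporting:** specify one table by arm, for the DSMB and the final report, that shows these two items beside the existing birth outcomes.
4. **Sections 8.3.2, 8.3.3.3 and 8.3.4:** reconcile the recording rules, including what happens when a complication of delivery meets a criterion for seriousness other than hospitalization.

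The cost is a few fields on the electronic form, filled from maternal and infant records that site staff already extract under Section 4.1, and slightly more abstraction time. The sample size, visit schedule and clinical care do not change. Because the source is the medical record, the fields could also be completed for women who have already delivered, if record access under their consent allows it.

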#### 8.3.4 TIME PERIOD AND FREQUENCY FOR EVENT ASSESSMENT AND FOLLOW-UP

The occurrence of an adverse event (AE) or serious adverse event (SAE) may come to the attention of study personnel during study visits and interviews of a study participant presenting for medical care, or upon review by a study monitor.

All AEs, not otherwise precluded per the protocol, will be captured on the appropriate case report form (CRF). Information to be collected includes event description, time of onset, clinician's assessment of severity, relationship to study procedures (assessed only by those with the training and authority to make a diagnosis), and time of resolution/stabilization of the event. All AEs occurring while on study will be documented appropriately regardless of relationship. All AEs will be followed to adequate resolution.

Any medical or psychiatric condition that is present at the time that the participant is screened will be considered as baseline and not reported as an AE. However, if the study participant's condition deteriorates at any time during the study, it will be recorded as an AE.

At each study visit, the investigator will inquire about the occurrence of AE/SAEs since the last visit.

---

#### 8.3.5 ADVERSE EVENT REPORTING

AEs will be recorded as part of the participants study record and entered into the data capture system. They will be reported to the Data and Safety Monitoring Board (DSMB)

---

#### 8.3.6 SERIOUS ADVERSE EVENT REPORTING

All SAEs will be reported to [name] (at Yale) or Drs. [name] or [name] (at UMass) for evaluation. Local IRBs will be notified by the site investigator according to local policy. They will be reported to the Data and Safety Monitoring Board (DSMB)

### 8.3.7 EVENTS OF SPECIAL INTEREST

N/A

## 8.4 UNANTICIPATED PROBLEMS

### 8.4.1 DEFINITION OF UNANTICIPATED PROBLEMS

This protocol uses the definition of Unanticipated Problems as defined by the Office for Human Research Protections (OHRP). OHRP considers unanticipated problems involving risks to participants or others to include, in general, any incident, experience, or outcome that meets all of the following criteria:

- Unexpected in terms of nature, severity, or frequency given (a) the research procedures that are described in the protocol-related documents, such as the Institutional Review Board (IRB)-approved research protocol and informed consent document; and (b) the characteristics of the participant population being studied;
- Related or possibly related to participation in the research (“possibly related” means there is a reasonable possibility that the incident, experience, or outcome may have been caused by the procedures involved in the research); and
- Suggests that the research places participants or others at a greater risk of harm (including physical, psychological, economic, or social harm) than was previously known or recognized.]

### 8.4.2 UNANTICIPATED PROBLEMS REPORTING

The investigator will report unanticipated problems (UPs) to the reviewing Institutional Review Board (IRB) according to local policy and to Drs. [name], [name] and [name]. The UP report will include the following information:

- Protocol identifying information: protocol title and number, PI's name, and the IRB project number
- A detailed description of the event, incident, experience, or outcome
- An explanation of the basis for determining that the event, incident, experience, or outcome represents an UP
- A description of any changes to the protocol or other corrective actions that have been taken or are proposed in response to the UP

To satisfy the requirement for prompt reporting, UPs will be reported to Drs. [name], [name] and [name] within 24 hours of becoming aware of the event. This will be compiled and provided to the DSMB at regularly scheduled meetings or within 24 hours if they are serious AEs.

